1 **Background:** Glioma imaging, used for diagnostics, treatment planning and follow-up, is
2 currently based on standard magnetic resonance imaging (MRI) modalities (T1 contrast-
3 enhancement for gadolinium-enhancing gliomas and T2/ Fluid attenuated inversion
4 recovery (FLAIR) hyperintensity for non-enhancing gliomas). The diagnostic accuracy of
5 these techniques for the delineation of gliomas is suboptimal.

6 **Objective:** To assess the diagnostic accuracy of advanced neuroimaging compared with
7 standard MRI modalities for the detection of diffuse glioma infiltration within the brain.

8 **Methods:** A monocenter, prospective, diagnostic observational study in adult patients
9 with a newly diagnosed, diffuse infiltrative glioma undergoing resective glioma surgery.
10 Forty patients will be recruited in three years. Advanced neuroimaging will be added to
11 the standard preoperative MRI. Serial neuronavigated biopsies in and around the glioma
12 boundaries, obtained immediately preceding resective surgery, will provide
13 histopathologic and molecular characteristics of the regions of interest, enabling
14 comparison with quantitative measurements in the imaging modalities at the same
15 biopsy sites.

16 **Expected outcome:** We hypothesize that a combination of positron emission
17 tomography, MR spectroscopy and standard MRI will have a superior accuracy for
18 glioma delineation compared to standard MRI alone. In addition, we anticipate that
19 advanced imaging will correlate with the histopathologic and molecular characteristics
20 of glioma.

21 **Discussion:** In this clinical study, we determine the diagnostic accuracy of advanced
22 imaging in addition to standard MRI to delineate glioma. The results of our study can be
23 valuable for the development of an improved standard imaging protocol for glioma
24 treatment.

25

26 **General information**

27 The study is titled: 'Frontiers in advanced imaging of unexplored glioma regions
28 (FRONTIER study)' (www.trialregister.nl, unique identifier NTR5354). Overall study
29 dates are September 2014 to September 2017. Funding agencies: Cancer Center
30 Amsterdam and the Dutch Cancer Society.

31 Investigation site: VU University Medical Center (VUmc), [name]
32 Amsterdam, The Netherlands.

33 Principle investigator: [name], PhD, Department of Neurosurgery.

34 Investigators: [name], MD, PhD, and [name], MD, Department of

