35 Neurosurgery; [name], MD, PhD, Department of Neurology; [name], MD,
36 PhD, Department of Pathology; [name], PhD, Department of Physics & Medical
37 Technology; [name], MD, PhD, [name], MSc, PhD and [name], MD, PhD,
38 Department of Nuclear Medicine & PET Research.

39

40 **Rationale and background information**

41 Gliomas represent 80-90% of parenchymal brain tumors in adults with an incidence of
42 5.9 per 100.000 person-years: approximately 1000 patients per year in The
43 Netherlands. ¹ Most gliomas show extensive infiltration in the brain parenchyma. These
44 so-called diffuse gliomas universally recur, without exception resulting in death despite
45 standard treatment, which consists of as extensive as possible resection, followed by
46 radiation and chemotherapy.

47 Both resective surgery and adjuvant radiation therapy are based on T1 contrast-
48 enhancement for gadolinium-enhancing gliomas and on T2/ Fluid attenuated inversion
49 recovery (FLAIR) hyperintensity volume outlines for non-enhancing gliomas. This
50 strategy is founded on early and preliminary observations, and has remained unchanged
51 since. ^{2,3} Diffuse gliomas recur locally in the vast majority of patients, even after
52 seemingly radical surgical removal and radiation therapy with 2 cm margins. This, and
53 the fact that glioma infiltration has been demonstrated to extend up to two centimeters
54 beyond standard MRI outlines, underscores that up till now delineation of these
55 neoplasms has been less than optimal. ⁴⁻⁷

56 Several publications provide arguments for underestimation of the spread of diffuse
57 gliomas using standard MRI and potential benefit from advanced MRI and positron
58 emission tomography (PET) imaging. Advanced imaging, such as diffusion-weighted
59 imaging (DWI), perfusion-weighted imaging (PWI), magnetic resonance spectroscopy
60 (MRS) and PET, has been shown to be able to identify tumor in areas of normal standard
61 MRI signal. ⁸⁻¹⁰

62 Our study addresses a clinically relevant research question, which so far has not been
63 adequately answered: What is the best neuroimaging approach to discriminate areas
64 with glioma infiltration from brain tissue without glioma cells?

65

66 **Study Goals and Objectives**

67 The goal of this study is thus to determine the best neuroimaging approach for glioma
68 delineation.

69 The specific objectives are:

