- 70 - To assess the increase in diagnostic accuracy of adding advanced neuroimaging
71 modalities to standard MRI for the detection of diffuse glioma infiltration within
72 the brain
- 73 - To correlate the information obtained by standard and advanced imaging to
74 histologic and molecular characteristics of the tissue.

75 We hypothesize that advanced neuroimaging, in combination with standard MRI, will
76 have a superior diagnostic accuracy in comparison with standard MRI alone. Besides, we
77 hypothesize that histological and molecular characteristics of (different areas of) glioma
78 will correlate better with advanced imaging than with standard imaging.

79

80 **Study Design**

81 The study design is a monocenter, prospective, diagnostic observational study.

82

83 **Methodology**

84 Subjects

85 *Inclusion criteria*

86 Patients of 18 years and older with a MRI interpretation of a diffuse glioma by an
87 experienced neuroradiologist, and who have an indication for resective surgery; the
88 indication confirmed by the multidisciplinary neuro-oncology tumor board.

89

90 *Exclusion criteria*

91 Patients who are pregnant or have undergone previous brain surgery, cranial irradiation
92 or chemotherapy. Patients with other brain pathology on MRI, such as stroke or multiple
93 sclerosis. Patients with a tumor located infratentorially or in the spinal cord.

94

95 *Withdrawal criteria*

96 Patients who do not successfully undergo one PET scan. A summary of all criteria is
97 given in table 1.

98

99 Study description

100 The study is separated into two phases (Figure 1). In both phases, standard and
101 advanced imaging will be performed pre-operatively (Table 2). Immediately preceding
102 resective surgery, serial image-guided neuronavigated biopsies in and around the
103 glioma boundaries will be obtained using a stereotactic drilling technique.¹¹ Two
104 samples are collected from each biopsy location, one for assessment of histopathologic
105 characteristics and one for molecular analysis.

106 Phase I is designed to decide on the optimal PET tracer, to simplify PET scanning
107 methodology and to develop a robust MRI protocol for glioma volume estimation. Eight
108 patients will receive a dynamic PET protocol with invasive blood sampling, and image-
109 derived carotid input function for metabolite analysis of
110 [18F-]Fluoroethyl-tyrosine (FET) and [11C-]Choline (CHO) tracers, as well as advanced

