183 events (SAEs) will be reported through the web portal ToetsingOnline
184 (<https://www.toetsingonline.nl>) to the accredited Medical Ethical Committee (METC)
185 that approved the protocol. SAEs that result in death or are life threatening are reported
186 expeditiously.

187

188 **Follow-up**

189 All patients will receive standard follow-up, which consists of postoperative clinical
190 admission for as long as needed and an outpatient appointment eight weeks after the
191 procedure. Apart from that, postoperative adjuvant chemo- and/or radiotherapy will be
192 installed according to histopathologic and molecular classification of the tumor, as
193 discussed postoperatively at the neuro-oncology tumor board meetings. All adverse
194 events will be followed until they have abated, or until a stable situation has been
195 reached.

196

197 **Data Management and Statistical Analysis**

198 Data will be collected on electronic CRF (eCRF). The eCRF is only assessable by the

199 principal and the study investigator. The eCRF will be completed on site by an
200 investigator. The principal investigator will review the collected data.
201 The number of biopsies and patients required to compare the area under the curve
202 (AUC) of the receiver operating characteristic (ROC) curves depend on the reference
203 AUC (t1), the minimal relevant AUC from the improved imaging (t2), the ratio of non-
204 tumor and tumor biopsies (ratio), the correlation of imaging within patients (r), the
205 average number of biopsies per patient (s), the correlation of histopathologic
206 quantification between biopsies within patients (rho), the type I error (alpha) and the
207 type II error (beta) ²¹⁻²³. Under the assumptions of t1 0.6, t2 0.8, ratio 0.25, r 0.5, s 6, rho
208 0.2, alpha 0.05 and beta 0.2, 20 patients per glioma target volume subgroup are
209 required. The overall study population then comprises 20 non-enhancing and 20
210 enhancing glioma patients, each stratum providing at least 120 biopsies. For testing the
211 correlation between simplified and full quantitative measurement of input function in
212 dynamic PET scanning a sample size of eight is mostly used in pilot studies. Due to the
213 experience with other trials we will include this number in phase I. In phase II 32
214 patients will be included to obtain the total of 40 patients from our sample size
215 calculation.
216 Continuous variables will be described as a mean with standard deviation if the

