217 distribution is symmetric and as a median with minimum and maximum if it is skewed.
218 Categorical variables are presented as numbers with percentages. Data analysis will be
219 performed using R. AUCs are compared using a nonparametric resampling test using
220 pROC in R. ²⁴⁻²⁶ Next, multivariate logistic regression analysis modeling histopathology
221 by quantitative imaging is performed using Bayesian models.

222

223 **Quality Assurance**

224 As the METC of VU University Medical Center (VUmc) decided it was unnecessary to
225 appoint a Data Safety Monitoring Board for this study, the progress of this study will be
226 monitored by the Clinical Research Bureau of VUmc.

227

228 **Expected Outcomes of the Study**

229 We expect that advanced imaging in combination with standard imaging, will have a
230 superior diagnostic accuracy for glioma delineation compared with current standard
231 imaging. This delineation could help neurosurgeons, neurologists, radiation oncologists

232 and medical oncologists in their clinical decision-making. Next, studies comparing
233 glioma resection or radiotherapy using standard versus standard plus advanced imaging
234 can be conducted to investigate possible influences on clinical outcome.
235 The expected correlation between advanced imaging and histologic and molecular
236 characteristics could provide biomarkers for prognosis and choice of therapy, as well as
237 further insight into glioma imaging

238

239 **Duration of the Project**

240 We anticipate that phase I will take 12 months and phase II 24 months, aiming for a total
241 study duration of three years.

242

243 **Project Management**

244 The principal investigator, [name], will lead the study. [name] will be
245 responsible for the MRS data, [name] for the MRI data, [name] and Dr.
246 [name] for the PET data, and [name] for the pathology data. The study
247 investigator, [name], MSc, will coordinate the logistics and of the study as well as
248 the interpretation of the results.

249

250 **Ethics**

251 The study is approved by the METC of VUmc and will be conducted according to the
252 principles of the Declaration of Helsinki and in accordance with the Medical Research
253 Involving Human Subjects Act. Explicit written consent will be obtained from all patients
254 in this study.

255 **Disclosures**

256 Financial support was provided by grant CCA2012-2-05 of the Cancer Center

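### The hypothesis concerns a combination of modalities, but the protocol neither links its AUC test to a fitted combination nor states a correction for optimism

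*Protocol*

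**What the plan says.** The abstract (Expected outcome) names the combination: positron emission "tomography, MR spectroscopy and standard MRI will have a superior accuracy for" delineation than standard MRI alone. Study Goals and Objectives makes the same contrast the first objective, "To assess the increase in diagnostic accuracy of adding advanced neuroimaging" modalities to standard MRI. The overall aim is wider: "The goal of this study is thus to determine the best neuroimaging approach for glioma" delineation.

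Data Management and Statistical Analysis sizes the study for a comparison of two AUCs: "Under the assumptions of t1 0.6, t2 0.8, ratio 0.25, r 0.5, s 6, rho" "0.2, alpha 0.05 and beta 0.2, 20 patients per glioma target volume subgroup are" required. The result is 20 non-enhancing and 20 "enhancing glioma patients, each stratum providing at least 120 biopsies".

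The same section gives the analysis in two steps. Data analysis is "performed using R. AUCs are compared using a nonparametric resampling test using" pROC. Then: "Next, multivariate logistic regression analysis modeling histopathology" by quantitative imaging, with Bayesian models. The text does not say which score represents the combination in the AUC test, which parameters enter the regression, what prior is used, or whether the fitted model is assessed on resampled or separate data.

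**The concern.** A combination of modalities has no AUC until some rule turns it into one score. The only such rule in the protocol is the regression, and that comes after the AUC test. This leaves two readings, and neither gives a sound test of the hypothesis.

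- **Written order.** No combined score exists yet when AUCs are compared, so the test covers single parameters. That is a different question from whether adding advanced imaging to standard MRI helps.
- **Fitted combination enters the test.** The larger model is compared with standard MRI on the biopsies that produced its coefficients. The tests cited for pROC resample or permute two given scores. They do not refit the model, so they leave its optimism in place.

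The protocol hopes the result will support an improved standard imaging protocol and later comparative studies of resection and radiotherapy. A gain that is partly overfitting would be a weak basis for either.

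**Working it through.** **1. The plan's own figure.** Inputs from the sample-size paragraph: t1 = 0.6, t2 = 0.8, ratio R = 0.25, r = 0.5, s = 6, rho = 0.2, alpha = 0.05, beta = 0.2. With the Hanley-McNeil variance per tumour biopsy,

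V(t) = [t/(2−t) − t²]/R + [2t²/(1+t) − t²],

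- V(0.6) = 0.0686/0.25 + 0.0900 = 0.364
- V(0.8) = 0.0267/0.25 + 0.0711 = 0.178
- Variance of the difference = 0.364 + 0.178 − 2 × 0.5 × √(0.364 × 0.178) = 0.288
- Tumour biopsies before clustering = (1.960 + 0.842)² × 0.288 / 0.20² ≈ 56.4
- Tumour biopsies per patient = 6/1.25 = 4.8; design effect = 1 + 3.8 × 0.2 = 1.76
- Patients = 56.4 × 1.76 / 4.8 = 20.7

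So 20 per subgroup is reproducible under this reading and some other standard ones. Two-sided readings that apply a design effect of 2.0 over all six biopsies give 23.5 to 29.8. Every version treats 0.8 as the AUC of a fixed test. None allows for model fitting.

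**2. Data per stratum.** 20 × 6 = 120 biopsies. At ratio 0.25, 120/1.25 = 96 are tumour and 24 are non-tumour. Both strata pooled give 192 and 48.

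**3. Number of parameters (assumption).** Table 2 is not shown. Its caption expands T/N ratio, Cho, NAA, CBF, FA, ADC, CBV and SUV, so 8–10 is plausible if every modality enters. The combination named in the abstract implies about 2–3.

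**4. Gain from noise alone.** Standard MRI is simulated as one normal score with true AUC 0.60, plus k parameters of pure noise. A logistic model is fitted and scored on the same biopsies, then compared with standard MRI by a two-sided 5% DeLong test, which stands in for the pROC resampling test. Separate runs agreed to within about 0.01 in mean gain.

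| k | Stratum (96/24): mean gain | Falsely significant | Pooled (192/48): mean gain | Falsely significant |
|---|---|---|---|---|
| 2 | 0.04 | 1–2% | 0.02 | 1% |
| 3 | 0.05 | 3–4% | 0.03 | 2% |
| 5 | 0.08 | 10–11% | – | – |
| 8 | 0.11 | 25–32% | about 0.065 | about 20% |
| 10 | 0.13 | 40–45% | about 0.075 | 31–37% |

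The planned gain is 0.8 − 0.6 = 0.20, so 0.11–0.13 is 55–65% of it.

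**5. Sensitivity, per stratum.**
- Parameters correlated within patient (assumed ICC 0.5): 0.14 with 8 and 0.17 with 10 (53% and 68% falsely significant).
- Best pair of 8–10 chosen on the same data: 0.09 (13%). Best triple of 8: 0.10 (27%).
- Normal priors with SD 0.5–2.5 left the gain at 0.08–0.09 with 5 parameters and 0.13–0.14 with 10, so a Bayesian fit with a weak prior does not remove it.

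**6. With correction.** A patient-level bootstrap optimism correction brought the noise gain to between −0.02 and +0.02 per stratum and between −0.02 and 0.00 pooled. In independent new data the noise models lost 0.03–0.06 (stratum) and 0.01–0.05 (pooled).

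**The case against.** The protocol never says that a fitted score is tested on its own fitting data. A reader might infer that an invalid in-sample comparison without validation is planned, but that is read from silence. Cross-validation or optimism correction is often left to a statistical analysis plan, and none is shown here. On the written order the AUC test comes before any fitted combination, so the simulation would not apply to it. This objection stands. What remains on that reading is the mismatch between test and hypothesis, which lies in the protocol's own text.

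A reader might also infer that the noise gain is bound to be large. The documents do not support that. The Table 2 caption is a list of abbreviations, not of predictors, and the protocol states no best-subset selection. Phase I reduces PET to one tracer, and the combination in the abstract suggests 2–3 added parameters. If these are fixed in advance, the false-positive rate stays below 5%. Even with 8 parameters, noise reaches the full 0.20 in only 7% of runs, and with 10 in 11–13%. This also stands. But the protocol fixes neither the list nor its length, and an aim of finding the best approach invites a choice among many.

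Finally, strong shrinkage could limit the optimism. No prior is stated, and the priors tried did not help.

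**Conclusion.** The concern holds as a gap between hypothesis and analysis. The protocol's hypothesis is about standard MRI plus advanced imaging, and its stated AUC test is not tied to any such combination. Taken in order, the test answers a single-parameter question. If a fitted combination is put into it, nothing stated removes the optimism.

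The size is conditional: negligible to small with 2–3 prespecified parameters, and more than half of the planned gain with 8–10 in one stratum. Pooling both strata reduces the 8–10 case to about 0.06–0.08, with roughly 20–37% falsely significant. These figures rest on an assumed parameter count, normally distributed markers, one score for standard MRI and the DeLong test as a stand-in. They do not show that the trial will report a spurious gain, nor that 20 patients per subgroup is miscalculated. Severity is moderate and confidence medium.

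**What to change.** In Data Management and Statistical Analysis:

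1. Name the primary AUC comparison: the standard MRI model against the standard plus advanced imaging model.
2. Prespecify a short list of parameters for each model, and the prior for the Bayesian fit.
3. Report the AUC difference corrected for optimism. Resample patients with all their biopsies kept together, repeat the whole fit and any parameter selection in each resample, and subtract the mean optimism. Give a patient-level bootstrap interval.
4. Show uncorrected AUCs as descriptive only.

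Repeated cross-validation with patients kept together is an alternative, provided both models are treated alike. In the simulations, a single tenfold run that pooled predictions and cross-validated only the combined model gave noise gains of −0.07 to −0.13, lower than the loss in new data. The bootstrap is therefore the better supported choice here.

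The cost is computing time, some protocol wording and a less favourable reported gain. No extra patients, scans or biopsies are needed.
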